3.2 Primary outcome

The "healthy baby" composite consists of the following 4 components:

- 1. Live baby (i.e. no pregnancy loss before 24 completed weeks, no stillbirth after 24 completed weeks of pregnancy and no neonatal death within 28 days of the birth)
- 2. Born at term (≥ 37 weeks + 0 days)
- 3. Appropriate weight for gestational age (GROW centile >9.99 & <90.01)*
- 4. Not admitted to a neonatal care unit (which includes Intensive Care Unit, SCBU and High Dependency Unit, but NOT transitional care)

A baby is considered a "healthy baby" only if the answer to all above questions is "yes", otherwise "no" (binary outcome measure). The primary outcome will be considered missing if any of its components are missing apart from the following exception: If Live baby is recorded as 'no' then the healthy baby outcome is 'no' regardless of whether other components are missing.

* The GROW centile macro version 8.0.6.2 will be used for component 3. Appropriate weight for gestational age. It is multidimensional and includes: maternal height and weight, ethnic origin, parity at booking, gestational age, baby alive (yes/no), baby gender and weight (g).

Note: at the grant application stage, the secondary outcome, spontaneous vaginal delivery (SVD) was defined as the primary outcome for the trial. However, following advice from and discussion with various stakeholders the "healthy baby" composite outcome was deemed a more suitable primary outcome for this project and chosen prior to commencement of the trial.

3.3 Secondary Outcomes*:

- 1. Spontaneous vaginal delivery (SVD)** defined as a woman who delivers vaginally (binary: for SVD, yes favoured)
- 2. Women's empowerment using pregnancy-related empowerment scale (continuous: sum of individual items with scores ranging from 16-64; higher scores are favoured)
- 3. Women's satisfaction with maternity care using *NHS* Friends and family test (continuous: score on one question with scores ranging from 1-5; lower scores favoured)
- 4. Breast feeding initiation (binary: did mother ever initiate breastfeeding, yes favoured --> however, possible different responses for descriptive analysis)
- 5. Mental wellbeing using Short Warwick-Edinburgh Mental Wellbeing Scale (continuous: total score ranges from 7-35, higher scores indicate higher positive mental wellbeing)
- 6. Live baby (i.e. no pregnancy loss before 24 completed weeks, no stillbirth after 24 completed weeks of pregnancy and no neonatal death within 28 days of the birth) using health records (binary: yes favoured)
- 7. Born at term (37 weeks + 0 days and above) using health records (binary: yes favoured)

- 8. Appropriate weight for gestational age (GROW centile >9.99 & <90.01) using health records (binary: yes favoured)
- 9. Not admitted to a neonatal care unit (which includes Intensive Care Unit, SCBU and High Dependency Unit, but NOT transitional care using health records binary: yes favoured)
- * Those for whom the primary outcome composite healthy baby variable is 'no' will inevitably have a lower response rate for the first follow up questionnaire. This is because the composite includes whether a baby is alive and born at term (i.e. at 37+ weeks gestation). Participants who have experienced pregnancy loss (baby alive = no) are not sent the first (or second) follow up questionnaire. Participants who deliver prematurely (<35 weeks) will not have had the opportunity to complete the first follow up questionnaire before delivery and are unlikely to complete it after. Analyses of variables collected via the follow up questionnaire, such as empowerment, satisfaction with care, self-efficacy, pre-natal stress, health literacy and emotional well-being, will acknowledge the exclusion of these groups, particularly if it is found that the intervention does have a significant effect on the primary outcome.
- ** Routine data will be used as the default source of data for SVD. We will use second follow-up SVD data only if routine data values for a participant are missing.

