5.5 General analysis principles

The analysis of primary, secondary, and, where possible, additional outcomes will be adjusted for the stratification factors which were used during randomisation, centre, and ability to speak English, only. All main analyses will be performed on a complete case basis (ignoring missing data) for the outcomes in question. A missing category will be created for the only covariate in the models "ability to speak English". The significance for statistical tests (alpha) will be 5%, all confidence intervals will be presented at the 95% level and all p-values will be two-sided. As the intervention arm includes group pregnancy circles, clustering will be accounted for in the intervention arm using pregnancy

circles as the units of clustering, while participants in the control arm will be modelled as a cluster size of one [1].

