5.10 Missing Data

For the analysis of the primary and secondary outcomes we assume that the data are missing completely at random. Sensitivity analysis to this assumption will be explored in sensitivity analyses for the primary outcome using multiple imputation (6). Further details are provided in the sensitivity analysis section. Moreover, we will only consider the primary outcome for women in the situation where all of its components are non-missing (i.e. available complete-case analysis).

The primary outcome is comprised of routine birthing data. The study team's commitment to attempt to locate and follow-up women with missing data has contributed to decrease this proportion as much as possible.

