5.16 Sensitivity analyses

5.16.1 Imputation analyses assessing the uncertainty around the primary outcome analysis estimate

To assess the extent to which study results are affected by missing data, a sensitivity analysis will be performed on imputed data for primary clinical outcome and stratification variables plus baseline characteristics: age, ethnicity, main language and educational level (2). The proportion of missing values for each variable will be assessed using numerical summaries. Univariable associations between missing values of each variable and observed values of other variables will be examined to understand how reliably a missing value might be imputed (3). This will be performed by constructing separate logistic regression models after creating a binary indicator variable for each variable with missing values coded as "1" and non-missing values coded as "0". The most applicable missing data mechanism will be informed by clinical knowledge of independent and dependent variables, reasons for missingness, and relationships between missingness and the observed values of collected variables.

Multivariate Imputation using Chained Equations (MICE) will be used to impute missing data under the expectation that both independent and dependent variables will have missing values and the data will not be monotonic missing (4). MICE replaces missing values with a random sample of plausible, imputed values drawn from their predictive distribution (5). First, an 'imputation' step will be performed, which involves constructing an imputation model that replaces missing data with one set of plausible values. Assuming that missing data are 'Missing At Random', the imputation model will specify a conditional distribution for missing values of each variable given the observed values of other variables. This imputation model will repeatedly replace missing values with a random sample of plausible values, creating a completed dataset with each imputation. The number of imputations (and thus completed datasets generated) will mirror the proportion of participants with at least one

missing value. For example, 25 complete datasets will be generated if 25% of study participants have at least one missing value (6).

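### Section 5.10 drops the Live baby exception made in 3.2, so the two sections define different primary analysis sets; known failures among live babies also become missing and open to imputation as healthy

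*SAP*

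**What the plan says.** SAP 3.2 defines a healthy baby by four components and gives 'yes' "only if the answer to all above questions is" yes, otherwise 'no'. The handling of gaps follows: "The primary outcome will be considered missing if any of its components are missing apart from the following exception". The exception applies when Live baby is 'no': "then the healthy baby outcome is 'no' regardless of whether other components are missing".

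SAP 5.10 describes the analysis set differently: "we will only consider the primary outcome for women in the situation where all of its components are non-missing". It does not mention the exception. The same section says "we assume that the data are missing completely at random", and SAP 5.5 adds: "All main analyses will be performed on a complete case basis (ignoring missing data) for the outcomes in question".

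The sensitivity analysis in SAP 5.16.1 uses "imputed data for primary clinical outcome and stratification variables plus baseline characteristics". It does not say what happens to a woman whose composite is coded missing although one of her recorded components has already failed.

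**The concern.** There are two separate problems.

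**The analysis set.** A pregnancy loss may well have no GROW centile and no neonatal-admission value. Under 3.2 that woman is a failure; under 5.10 she is not analysed. Two analysts, each following one section, could report different primary denominators. The estimand table in 5.8 makes pregnancy loss before or after 24 weeks part of the outcome variable, so 5.10 read literally also departs from the estimand. For such women the loss itself would cause the gap, which does not fit the assumption of data missing completely at random.

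**Known failures among live babies.** By the definition in 3.2, one observed 'no' settles the composite. The rule for gaps respects this for one component of four. A live baby recorded as preterm, or as admitted to a neonatal unit, becomes missing if the centile cannot be computed. The centile depends on several maternal, pregnancy and infant inputs, so this can happen. Because 5.16.1 imputes the composite as a whole, such a baby could be imputed as healthy.

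**Working it through.** **The rules side by side**

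| Record | By the definition | Rule in 3.2 | 5.10 read literally |
|---|---|---|---|
| Live baby 'no', centile or admission missing | no | no | not analysed |
| Live, preterm or admitted, centile missing | no | missing | not analysed |
| Live, three components 'yes', one missing | undetermined | missing | not analysed |
| All four recorded | determined | as recorded | as recorded |

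The first row is the contradiction between sections. The second is the loss of a known result.

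**Inputs.** The control rate of 69% and the difference of 8 points, hence 77% with the intervention, come from SAP 4.1.1. These rates reproduce the planned size closely. Two proportions at two-sided 5% and 90% power need 646 per arm. A design effect of 1 + ((1 + 1/8) × 8 − 1) × 0.05 = 1.40 in the intervention arm only gives 769, and 769/0.9 = 855 per arm, against 866 stated. The sample size is not in dispute. Rates of loss and of component missingness are not in the SAP and are assumed below.

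**Step 1: effect of 5.10 on losses.** Let L be the share of women lost with another component missing. They are all failures, so dropping them turns a healthy rate p into p/(1 − L).

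| L control | L intervention | Control | Intervention | Difference |
|---|---|---|---|---|
| 0 | 0 | 69.0% | 77.0% | 8.0 |
| 1% | 1% | 0.69/0.99 = 69.7% | 0.77/0.99 = 77.8% | 8.1 |
| 2% | 2% | 0.69/0.98 = 70.4% | 0.77/0.98 = 78.6% | 8.2 |
| 3% | 3% | 0.69/0.97 = 71.1% | 0.77/0.97 = 79.4% | 8.2 |
| 3% | 1% | 71.1% | 77.8% | 6.6 |

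Equal losses raise both rates and leave the difference almost unchanged. Unequal losses take part of the effect out of the composite.

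**Step 2: the 3.2 rule among live babies.** If gaps are unrelated to outcome, dropping every woman with a gap leaves 69% and 77% unchanged; only information is lost. If gaps occur in a share g of failures and h of successes, the rate becomes p(1 − h) / [p(1 − h) + (1 − p)(1 − g)]. With g of 5-20% and h of 0-5%, the control rate is 69.0-73.6% and the difference 7.2-8.0 points. The extreme is g = 20%, h = 0: 0.69/0.938 = 73.6% and 0.77/0.954 = 80.7%.

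**Step 3: scoring 'no' on any observed 'no', without imputation.** Let the centile be missing at random in a share f of women, and let a share q of failures be identifiable from the other components. The rate becomes p(1 − f) / [(1 − f) + (1 − p)fq].

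- f = 2%, q = 30%: control 0.6762/0.98186 = 68.9%, intervention 76.9%.
- f = 10%, q = 50%: control 0.6210/0.9155 = 67.8%, intervention 76.0%.

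The control rate falls by about 0.1-1.2 points. The difference is 8.0 points in the first case and 8.2 in the second.

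**The case against.** The best defence is that 3.2 is the specific definition and 5.10 a loose summary of it. The footnote to 3.3 treats pregnancy loss as a case where the composite is 'no', and the estimand table agrees, so the intention can be recovered. That stands as a reading of intent, and it is why one sentence cures the conflict. It does not remove the conflict: 5.10 is worded as a restriction on who is analysed, and SAP 1.6 ranks the SAP above earlier documents without ranking its own sections.

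Three stronger readings are tempting, and the SAP does not support them.

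- *All losses would leave the analysis.* Only losses with another component missing would. The SAP does not say how centile and admission are recorded after a loss, and a stillbirth or neonatal death with every field filled would stay in.
- *The 3.2 rule makes missingness depend on the outcome among live babies.* It sets a woman with a gap to missing whether her other components passed or failed. Under the stated assumption of data missing completely at random, that is unbiased among live babies. The rule that scores any observed 'no' is the outcome-dependent one when used alone in a complete-case analysis (step 3).
- *Allocation is left out of the imputation, which pulls the result towards no effect.* The list in 5.16.1 names data to be imputed, and allocation is known for every randomised woman. The section conditions on observed values of other variables and describes auxiliary variables as additional to those in the analysis, which suggests that analysis variables are already included. Site is covered as a stratification factor. Allocation and circle are simply not named, which calls for a clarification.

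**Conclusion.** The contradiction between 3.2 and 5.10 is real and concerns who enters the primary analysis. Its numerical effect cannot be fixed from the SAP. On the planning rates it is negligible for the risk difference if losses of 1-3% are equal between arms, and it reaches 1.4 points (8.0 to 6.6) if losses are 3% in control and 1% in intervention. That last case assumes a threefold imbalance, with every loss lacking another component.

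The treatment of live babies with an observed failure is a weaker point. The 3.2 rule conflicts with the logic of its own definition and discards information, but it is defensible in a complete-case analysis if gaps are completely at random. The firmer objection is to 5.16.1, which does not prevent a known failure from being imputed as healthy.

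**What to change.** 1. In 5.10, repeat the Live baby exception from 3.2, so that both sections give the same analysis set.
2. In 5.16.1, impute the missing components and derive the composite from them. Wherever an observed component has failed, keep the composite at 'no'. State that allocation and circle are in the imputation model.
3. Decide, and record, whether the primary derivation stays as in 3.2 or is extended to 'no' whenever any observed component is 'no'. If it is extended, report it with the component-level imputation, because alone it lowers the healthy rate slightly. The existing Live baby exception has the same asymmetry.

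The cost is a few sentences in a SAP amendment and some lines of derivation and imputation code. No extra data are needed and the sample size does not change. It should be done while the analysts are still blinded, as SAP 4.3 provides until sign-off and database lock; settled later, it would be a choice made with results in view.

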3.4 Additional Outcomes

Additional outcomes have been included due to a) interest from the study team and b) to reflect those intermediate outcomes in the Pregnancy Circles logic model which are not included as secondary outcomes (see Wiggins et al., 2020). Additional outcomes have been listed separately from secondary outcomes to avoid multiplicity issues due to an excessive number of secondary outcomes and are to serve predominantly for hypothesis generation.

- 1. Social support using Duke Social Support Scale (continuous: scores range from 8-40, higher scores favoured)
- Self-efficacy using Perlin Mastery Scale (continuous: scores range from 7-28 with higher scores favoured)
- 3. Prenatal stress using Revised Prenatal Distress Questionnaire (continuous: 12-item total score, scores range from 0-16; higher is favoured)
- 4. Health literacy using Health Literacy Questionnaire (continuous: score on only first domain of HLQ, range 1-20, higher score favoured)
- 5. Attendance at antenatal care (continuous: number of sessions, higher is favoured)
- 6. Additional measures of satisfaction with care (categorical: (FU1) Overall, how do you feel about the care you received from midwives? Options very happy, fairly happy, not very happy, very unhappy; (FU2) Overall, how do you feel about the care you received from midwives (before the birth of your baby)? options very happy, fairly happy, not very happy, very unhappy)
- 7. Caesarean delivery (categorical: planned, emergency, none)
- 8. Infant birth weight in grams (continuous)
- 9. Place of birth (categorical: actual place of delivery; options= hospital obstetric unit, hospital alongside midwifery unit, freestanding midwifery unit, home or other)

- 10. Breast feeding continuation and exclusivity (binary: did mother exclusively breastfeed to 3-month follow-up, yes favoured --> however will look at exclusive, breast milk, artificial exclusive, mixed, other in descriptive analysis)
- 11. Postnatal depression using Edinburgh Postnatal Depression Scale (binary: mothers scoring above 13 are "likely to be suffering from a depressive illness of varying severity", no favoured)

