4.1 Sample size

4.1.1 Sample size calculation (pre covid)

For the primary outcome ("Healthy baby"), in order to detect a difference in babies born "healthy" of 8% between the control and intervention arm, with 90% power and a 5% significance level, we would require at least 866 women per arm (i.e. 1732 total). This calculation also assumed an outcome proportion of 69% in the control arm, accounts for clustering within the intervention arm with an intra-cluster correlation (ICC) of 0.05 (in the intervention arm), mean group sizes of 8 with cluster size variability assuming Poisson distribution and assumes 10% drop-out in both arms. This sample size provides 84.8% power to detect a difference between arms of 7.3% in our, former primary outcome, spontaneous vaginal birth. Thus, a sample size 1732 is sufficiently powered to detect changes in both the primary outcome and SVD (now a secondary outcome).

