Randomised under incorrect stratification factor			
Switched circle after 1 st session attended			
Incorrect allocation received			
Other			

Table 7: Adverse and serious adverse events

	N S	SAEs	partic experi	N ipants encing NEs	N unexpected SAEs related to N the intervention		N AEs		experi	cipants encing Es
	PC	UC	PC	UC	PC	UC	PC	UC	PC	UC
Site										
ASP										
BDH										
CLT										
EST										
EPS										
HAR										
HHT										
IPS										
LGT										
QEH										
NWH										
RFH										
RLH										
SAS										
STH										
WHH										
WHX										
WOR										

^{*}PC – Pregnancy circle, UC – Usual care

Table 8 – Results for subgroup analysis of primary outcome

	Number incl	uded in analysis	Healthy ba	aby - yes		
	PC*	UC*	PC*	UC*	OR 95%CI	p-value fo
	N	N	N (%)	N (%)		interactior **
Ethnicity						
White						
British						
White-Irish						
Other-White						
Black or						
Black British-						
Caribbean						
Etc						
Vulnerability						
Yes						
No						
Vulnerability						
index						
0						
1						
2						
3						
4						
5						

^{*}PC – Pregnancy circle, UC – Usual care

Table 9 – Results of Complier-Average Causal Effect analysis investigating the effect of the intervention on the Healthy baby outcome amongst compliers*

Estimator	N	OR 95%CI	RD 95%CI	p-value
ITT				
CACE				

^{*95%}CI, 95% confidence interval; ITT, intention-to-treat; CACE, complier-average causal effect

Table 10 – Results of dose-response relationship between primary outcome and number of antenatal care sessions attended

	Number included (N)	in analysis	Regression coefficient (β)	95%CI	P-value
N of antenatal					
care					
session(s)					

^{**} Likelihood ratio test when multiple categories

Table 11. Sensitivity analysis: multiple imputation of primary outcome and spontaneous vaginal delivery

	wonter y							
Outcome	n (%)	n (%)	OR 95%CI	OR	RD 95%CI	RD	P-value	P-value
	(complete	(multiply	(complete	95%CI	(complete	95%CI	(complete	(multiply
	case data)	imputed	case data)	(multiply	case	(multiply	case	imputed
		data)		imputed	data)	imputed	data)	data)
				data)		data)		

Health baby

Spontaneous vaginal delivery without instruments

Table 12. Sensitivity analysis: Results for primary analysis for multiple births considering 'Healthy Baby' composite equals 'yes' if at least one of the babies is healthy. Otherwise, Healthy baby equals 'no'.

	Number in analy		Summary measure		Treatment effect			

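### SAP section 3.3 defines spontaneous vaginal delivery as any vaginal delivery, while dummy Tables 2 and 11 report it as delivery without instruments

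*SAP*

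**What the plan says.** **Spontaneous vaginal delivery (SVD).** Section 3.3 lists it first among the secondary outcomes: "Spontaneous vaginal delivery (SVD) defined as a woman who delivers vaginally", a binary outcome with yes favoured. The footnote to that list deals only with provenance: "Routine data will be used as the default source of data for SVD", with the second follow-up used when the routine value is missing. The row label in dummy Tables 2 and 11 (section 8.4) is "Spontaneous vaginal delivery without instruments". Section 3.2 notes that SVD was the primary outcome at the grant application stage. Section 4.1.1 says: "This sample size provides 84.8% power to detect a difference between arms of 7.3% in our, former primary outcome, spontaneous vaginal birth".

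**Prenatal stress.** Section 3.4 describes the Revised Prenatal Distress Questionnaire as "12-item total score, scores range from 0-16; higher is favoured". Table 3 repeats the 0-16 range. The outcome is one of the additional outcomes, which "are to serve predominantly for hypothesis generation".

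**Neonatal unit.** Section 3.3 defines the outcome as not being admitted, with yes favoured. The matching row of Table 2 is labelled as admission, under a column giving the percentage of yes.

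**The concern.** A programmer who follows section 3.3 codes an instrumental birth as a success. One who follows Tables 2 and 11 codes it as a failure. Both would be following the signed-off plan, and they would produce different results for the first secondary outcome.

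Under the section 3.3 wording the word spontaneous does no work. Section 3.4 already has caesarean delivery as a separate outcome (planned, emergency, none), and the fallback in section 5.9 collapses it to any versus none. Apart from missing data, that collapsed variable is the section 3.3 version of SVD with the coding reversed. An effect of group care on the use of instruments, with caesareans unchanged, could not appear in the SVD result at all.

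Timing matters too. Section 4.3 keeps the analysts blinded until the SAP is signed off and the database is locked. If the conflict is still open then, the definition could be chosen with results in view.

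The other two entries matter less. A distress total described as better when higher, on a range that does not fit its number of items, invites a wrong sentence in the report. A component row that points the opposite way from its definition invites a misread odds ratio.

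**Working it through.** **1. The plan's own power figure.** The variance method was first checked on the primary sample size in section 4.1.1. Inputs: 69% versus 77%, 90% power, ICC 0.05, mean circle size 8 with Poisson variation, 10% drop-out; two-sided 5% (section 5.5).

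- Design effect, intervention arm only: 1 + [(1 + 1/8) × 8 − 1] × 0.05 = 1.40.
- Variance sum: 0.69 × 0.31 + 1.40 × 0.77 × 0.23 = 0.2139 + 0.2479 = 0.4618.
- n per arm: (1.960 + 1.282)² × 0.4618 / 0.08² ≈ 758. Dividing by 0.9 gives 843 (855 with a pooled variance under the null).

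The SAP states 866, so this agrees within 3%.

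The same variance was then applied to SVD, with n = 866 × 0.9 = 779.4 per arm, control rate p and intervention rate q = p + 0.073:

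power = Φ(0.073 / SE − 1.96), SE = √{[p(1 − p) + 1.40 q(1 − q)] / 779.4}

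The SAP gives no control rate for SVD, so p has to be assumed:

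| Assumed control rate | Power |
|---|---|
| 0.40 | 75.7% |
| 0.50 | 75.4% |
| 0.60 | 78.6% |
| 0.65 | 81.6% |
| 0.70 | 85.5% |
| 0.80 | 95.3% |

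The stated 84.8% corresponds to a control rate of about 0.69. It can be neither confirmed nor refuted, because neither the rate nor the definition behind it is given. The control rate depends on whether instrumental births count, so the power statement has no fixed meaning until the definition does.

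**2. What each definition estimates.** Let s, i and c be the proportions of spontaneous, instrumental and caesarean births in an arm, with s + i + c = 1, and let Δ be intervention minus control.

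- Tables 2 and 11: effect = Δs.
- Section 3.3 as worded: effect = Δs + Δi = −Δc.
- Difference between the two: Δi.

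Illustration (assumed, not from the SAP): 5 points move from instrumental to spontaneous birth and caesareans do not change. Then Δs = +5, Δi = −5 and Δc = 0. The tables' definition gives 5 points and the section 3.3 wording gives 0. If instead 5 points moved from caesarean to instrumental birth, the tables' definition would give 0 and section 3.3 would give 5. If Δi = 0, the two risk differences are equal, although the rates and odds ratios still differ.

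**3. Range of the distress total.** Twelve items each scored 0 to k, summed, run from 0 to 12k: 12, 24, 36, 48 or 60 for k = 1 to 5. Sixteen is not among them (16/12 = 1.33). The range fits only if the items are on unequal scales, which the SAP does not describe.

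**4. Direction of the distress total.** The SAP marks lower scores as favoured where it means that: the Friends and Family test in section 3.3 and postnatal symptoms in section 3.4. It describes no reverse scoring for prenatal distress.

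**The case against.** The strongest reply is that the intended meaning is plain. The outcome is called spontaneous, both results tables exclude instruments, and caesarean delivery is analysed separately, so section 3.3 is loose drafting rather than a decision. Much of that stands: a reader might infer that the SAP has settled on counting forceps and ventouse births as successes, and it has not. It contradicts itself. But the outcome section is where a programmer looks for the coding rule, and the rule there gives the wrong variable. The footnote covers only the source. The protocol, not examined here, may define the outcome more tightly, but SAP section 1.6 lets the SAP's analyses prevail in a discrepancy.

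On prenatal distress, a reader might infer that the conclusion would reverse sign. It would not. The model in section 5.9 estimates a mean difference, the test is two-sided, and the favoured direction enters neither, so only the interpretation is exposed. Nor can the 0-16 range be called impossible, because the item scoring is not given. No planned analysis uses the range.

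On Table 2, reporting admission instead of non-admission inverts the odds ratio and changes the sign of the risk difference without losing information. The table already mixes directions, since it includes postnatal depression. This is a matter of presentation.

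**Conclusion.** The contradiction on SVD is established from the SAP's text alone and needs correcting before the analysis. It affects the first secondary outcome, and the definition in section 3.3 is the wrong one of the two by the SAP's own table labels. The two effects differ by the between-arm difference in instrumental births, which the SAP gives no basis for estimating.

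Two stronger conclusions are tempting and are not supported. One is that the effect the trial was powered for is not the effect it will test. Section 4.1.1 states neither the definition nor the control rate behind the 84.8%, so this cannot be known. The other is to set a plausible overall share of instrumental births against the 7.3-point target. Reclassification that is equal in both arms is not comparable with a difference between arms; only a differential shift moves the risk difference.

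The distress direction and range and the Table 2 label are minor corrections. The direction is wrong on its face for a distress score without reverse scoring. The range is inconsistent with twelve equally scored items, but the correct one cannot be fixed from the SAP.

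**What to change.** - **Section 3.3:** define SVD as vaginal delivery without instruments, matching Tables 2 and 11, and state that the same rule applies to the routine data and to the second follow-up data.
- **Section 3.4:** change the favoured direction for the prenatal distress total from higher to lower.
- **Section 3.4 and Table 3:** check the 0-16 range against the instrument's scoring and correct both places together.
- **Table 2:** relabel the neonatal unit row as not admitted, to agree with section 3.3.

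The cost is a short SAP amendment and a check of the derivation code. No new data are needed if both sources record mode of birth in enough detail to separate instrumental from unassisted delivery, as the table labels imply; this should be confirmed for the second follow-up questionnaire. The amendment should be dated before unblinding or, if that has passed, should say so.
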